1. PURPOSE OF STUDY

Neuropsychiatric symptoms (NPS) are a distinctive set of behavioral disturbances that are prevalent in mild cognitive impairment (MCI) and Alzheimer's disease (AD), worsening of which, particularly, can accelerate patients' cognitive and functional decline and cause significant distress to caregivers.^{1,2} NPS often co-exist, rendering the need to understand the shared biological mechanisms underlying multiple NPS, which is crucial for the development of effective interventions to address them simultaneously. Notably, we recently discovered a neural circuit shared by MCI and AD patients with multiple NPS; the circuit is composed of 10 frontal-temporal-striatal regions³ and is highly related to both study partner-rated Neuropsychiatric Inventory Questionnaire (NPI-Q) and AD pathology (indexed by cerebrospinal fluid A β /ptau ratio).³ The **goal of this proof-of-concept mechanistic intervention study** is to confirm the causal relationship between this neural circuit and various NPS, by modifying a key region within the neural circuit [i.e. left precentral gyrus (LPG), critical for regulating visual attention⁴] with anodal transcranial direct current stimulation (tDCS).

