Why focus on the LPG via tDCS to understand the contribution of this shared neural circuit to NPS? Our previous work on NPS-shared neural circuit shows that while different NPS are associated with the same 10 frontal-temporal-striatal regions, the strength of functional connectivity (FC), as well as its directionality, varies for different NPS. For example, the strength of most FCs in MCI/AD patients with a depressive symptom is lower than that in patients without this symptom, while the strength of most FCs are higher in patients with an anxiety symptom. Across NPS, however, LPG is the only region that has lower FCs with frontal and striatal regions within the circuit whenever a NPS is present.³ LPG, parallel to C3 in the 10/20 EEG system,⁵ is one of the most frequently examined and effective tDCS targets modifying affective, psychiatric, and psychosomatic symptoms, in addition to motor function.⁶⁻⁸ Administering anodal tDCS also enhances the strength of FCs linking LPG to frontal and limbic regions that are part of the NPS-shared neural circuit.⁹⁻¹² Notably, our feasibility study demonstrated our readiness and safety of administering anodal tDCS to C3 in older adults. Synthesizing these separate lines of evidence, we **hypothesize** that administering anodal tDCS to C3 in patients with NPS will result in enhanced activation of LPG and reorganization of NPS-shared neural circuit, both of which will improve NPS.

Aim 1. Determine the effect of tDCS on NPS-shared neural circuit. **H:** After intervention, the active group, relative to the sham group, will have a greater increase in LPG activity, indexed by greater activation in LPG in response to a visual attention task (H1a) and greater increase in resting FC strength between LPG and other regions within the NPS-shared neural circuit (H1b).

Aim 2. Determine the relationship between NPS-shared neural circuit and study partner-report NPS. **H:** After intervention, the active group, relative to the sham group, will have greater improvement in study partner-rated NPS in terms of lower severity and fewer co-existing symptoms (H2a). Changes in LPG task-induced activity combined with an LPG-seeded NPS-shared neural circuit will contribute to the

improvement in study partner-rated NPS across groups (H2b).

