We propose to examine the influence of LPG, a region within the NPS-shared neural circuit and a region known to regulate visual attention, on the NPS-shared neural circuit and study partner-rated NPS. In the proposed study, we capitalize on a non-invasive brain stimulation process to manipulate the activation and FC strength seeded in LPG. This design will provide an understanding beyond the correlational relationship between the neural circuit and NPS in patients with MCI. TDCS non-invasively induces a low direct current in the cortical region of interest (ROI), with a potential neural mechanism of inducing synaptic changes that affect neural network activity, reflected in changes in both activation and strength of FC, as well as changes in visual attention-dominant tasks.³⁸ LPG is one of the primary tDCS targets for obtaining effects on psychosomatic and affective symptoms⁶⁻⁸; furthermore, tDCS can easily target (i.e., on the cortical surface) and modulate (i.e., produces large effects) the region. Applying an average of 20 minutes of continuous tDCS can yield acute effects for up to 90 minutes, while 2-4 weeks of sessions can yield effects for up to 6 months.³⁹⁻⁴² Most importantly, tDCS is safe and non-invasive, thus, these characteristics together make tDCS an ideal manipulation technique to modify LPG.

Scientific premise and hypothesis: This proposal aims to determine the causal relationship between our recently discovered NPS-shared neural circuit and study partner-rated NPS by stimulating a region within this circuit (LPG). We integrate the evidence from existing literature and our preliminary work that are potentially relevant to what is proposed here: (1) a worsening pattern of NPS in MCI is most

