17. DATA ANALYSIS PLAN

This is a pilot study for mechanistic understanding of the relationship between our previously discovered NPS-shared neural circuit and study partner-rated NPS. Results from the study will provide information for accurately calculating effect size for future clinical trial. Regardless, in addition to follow the rule of 12-20 subjects per group for a pilot clinical trial, we will calculate the sample size. The sample size calculation is based on the effect size of LPG related tDCS on visual attention performance ($f = 0.45$, $n = 36$). Additionally, the effect size of correlation between NPS-shared neural circuit and patient-report NPI-Q was $r^2 = 0.70$ in our previous study³ – here we use a much more conservative estimation at $r^2 = 0.20$, the sample size will be $n = 37$. All of these calculations are based on power at 0.80 and alpha at 0.05. For an 8-week follow up, we estimate 10% attrition rate. Therefore, we propose a total of 40 intervention subjects for the study.

Aim 1. Determine the effect of tDCS on NPS-shared neural circuit. H: After intervention, the active, relative to sham group will have greater increase in LPG activity, indexed by greater activation in LPG in response to visual attention task (H1a) and greater increase in resting FC strength between LPG and other regions within the NPS-shared neural circuit (H1b). To assess the activation pattern in LPG, we will conduct GLM analysis with the SPM software. The coefficients of GLM corresponding to LPG will be analyzed through hypothesis testing. We will first conduct a simple t-test to evaluate whether the intervention increases LPG activation for each group (at 4 or 8 weeks), and then a more powerful two sample kernel test will be used to test activations distribution difference between groups.⁵¹ Similarly, we will take the FCs between LPG and other regions as a multivariate covariate and apply the two-sample kernel test to evaluate group difference in the change of LPG FC pattern after intervention (at 4 or 8 weeks). In addition, simple multiple testing for each connection will be used as a screening procedure to identify a subset of connections included in the kernel test.

Aim 2. Determine the relationship between NPS-shared neural circuit and study partner-report NPS.

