H2a. After intervention, the active, relative to sham group will have greater improvement in study partner-rated NPS in terms of lower severity and fewer co-existing symptoms: We will fit linear mixed-effect models for changes in NPS: $Y_i = X_i\beta + Z_iu_i + \epsilon_i$, where $Y_i = (y_{i1}, \dots, y_{iT})$ represents the NPI measures across time, X_i is a $T \times p$ design matrix for the fixed effects and Z_i is a $T \times q$ matrix for the random effects. The models will include fixed effects such as data collection visit (categorical variable), group, visit and group interaction, and covariates identified as being imbalanced among groups. Stepwise variable selection based on Akaike Information Criteria will be used to select the fixed effects for inclusion. A random participant-specific effect will be included to account for correlation between visits for the same participant. The model-based average within-group change will be computed for each outcome at 4 and 8 weeks. This will allow us to rank the groups in terms of average within-person gains in each outcome. We will conduct a composite hypothesis test to assess if the changes at 4 or 8 weeks differ by groups (similar to a one-factor ANOVA but accounting for repeated measures). **H2b. FC change in NPS-shared neural circuit will contribute to the improvement in study partner-rated NPS across groups:** We will perform epsilon-intensive support vector regression (SVR) with RBF kernel using LIBSVM library.⁵² The Leave-One-Out-Cross-Validation scheme will be applied: each intervention subject will be designated as

the test sample once, while the remaining intervention subjects will be used as training sample. All training sample's features (change of voxel activation from the task or change of FCs from the NPS-shared neural circuit after intervention) will be trained to predict the test sample's outcome (change of NPI severity or frequency score). We will then perform model fitting of the raw and predicted NPI using linear function ($f(x)=ax+b$). Adjusted R^2 will be used to estimate goodness of fit for the model.

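### H2b is limited to LPG predictors in the aims but not in the analysis plan, so a good SVR fit need not test the LPG hypothesis

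*Combined protocol and SAP*

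**What the plan says.** Section 1 (Purpose of Study, Aim 2) words H2b in terms of LPG: "Changes in LPG task-induced activity combined with an LPG-seeded NPS-shared neural circuit will contribute to the" improvement in partner-rated NPS across groups.

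Section 17 (Data Analysis Plan, Aim 2) restates the hypothesis without LPG and without task activity: "FC change in NPS-shared neural circuit will contribute to the improvement in study partner-rated NPS across groups". The method is an RBF-kernel SVR with leave-one-out cross-validation. Its features are "change of voxel activation from the task or change of FCs from the NPS-shared neural circuit after intervention" and its outcome is "change of NPI severity or frequency score". Observed and predicted NPI are then related by a straight line, and "Adjusted R^2 will be used to estimate goodness of fit for the model".

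On the circuit itself, section 1 says that "the circuit is composed of 10 frontal-temporal-striatal regions", and section 2 confirms that LPG is one of them: "We propose to examine the influence of LPG, a region within the NPS-shared neural circuit".

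For Aim 1, section 17 restricts the analysis to LPG in so many words. On activation: "The coefficients of GLM corresponding to LPG will be analyzed through hypothesis testing". The connectivity features there are those linking LPG to the other regions.

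**The concern.** H2b is the planned analysis that links brain change to symptom change. Under the aims, a positive result would say that change in LPG activity and LPG-seeded connectivity goes with improvement in NPS. Under section 17 as written, the model may draw on task voxels outside LPG and on circuit connections that do not touch it.

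Nothing later in the plan separates the two. There is one goodness-of-fit figure, with no feature weights, no LPG-only model and no comparison of LPG with non-LPG features. Because H2b is assessed across groups, the active-versus-sham contrast does not tie a good fit to LPG either.

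The risk is that a good fit gets reported as support for the LPG hypothesis when that hypothesis was not what was tested. An analyst could also choose between the two feature definitions after seeing the data.

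**Working it through.** **1. The plan's own figure.** Section 17 gives n = 37 for the circuit–NPS correlation at r² = 0.20, power 0.80, alpha 0.05. Fisher z, two-sided:

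- r = √0.20 = 0.447; atanh(r) = 0.481
- n = ((1.960 + 0.842) / 0.481)² + 3 = 36.9, so 37

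The figure reproduces. It concerns a single correlation and does not depend on which features enter the SVR, so this point leaves it unchanged.

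**2. The two statements side by side.**

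| | Section 1, Aim 2 | Section 17, H2b |
|---|---|---|
| Task activation | in LPG | task voxels, no mask named |
| Connectivity | seeded in LPG | circuit connections, no seed named |
| Use of the two | combined | one or the other |
| Readout | not stated | adjusted R², across groups |

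**3. How many connections could be non-LPG.** Inputs: 10 regions (section 1), LPG one of them (section 2). Assumption: one undirected connection for each pair of regions.

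- All pairs: 10 × 9 / 2 = 45
- Pairs with LPG: 9
- Pairs without LPG: 9 × 8 / 2 = 36, and 36/45 = 80%

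The documents do not list the circuit's connections, so the share is not fixed. Counting both directions leaves it at 72/90 = 80%. If the circuit held only the 9 LPG connections it would be 0%. If LPG were linked to a single region and all other pairs were present it would be 36/37 = 97%. Zero is hard to square with section 1, which singles LPG out from the other circuit regions by its connectivity pattern. For voxels no count is possible, because no mask or voxel number is given.

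**4. Can the fit be good with no LPG contribution?** Simulation with assumed effects: n = 36 (40 less 10% attrition), 45 connections, the 9 LPG connections pure noise, the other 36 driven by two factors, and the outcome equal to one factor plus noise of SD 0.5 (so 1/1.25 = 80% of its variance comes from that factor). RBF epsilon-SVR with C = 1, leave-one-out, 60 runs:

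| Model | Median r, observed vs predicted | Median adjusted R² |
|---|---|---|
| 45 connections | 0.75 | 0.55 |
| 9 LPG connections | −0.06 | −0.01 |

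The signal is deliberately strong. This shows that the outcome is possible, not how likely it is.

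**5. Does restriction to LPG settle attribution?** Not if connections are correlated. With a common correlation of 0.2 between connections, signal only in non-LPG connections at R² = 0.20, and leave-one-out RBF kernel ridge standing in for SVR (5% null threshold), the 45-connection model was positive in 54% of trials and the 9-connection LPG model in 25%. At R² = 0.5 the LPG model was positive in 70%. If connections correlate only through shared regions, the LPG model's figure is 8–9%. The true structure is unknown.

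**The case against.** Section 17 omits an LPG restriction. It does not say that every voxel or every connection is used, and it may be shorthand for the LPG-seeded circuit of the aims. That is possible, but the same section names LPG explicitly for Aim 1 and drops it from the H2b heading, so a reader cannot assume the restriction.

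The connectivity features do match the hypothesis as section 17 restates it. This stands: the defect is two versions of H2b, not an SVR that departs from its own heading.

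A whole-circuit model is also a legitimate question. Sections 1 and 2 expect LPG stimulation to reorganize the circuit, the title of Aim 2 refers to the circuit, and LPG engagement is tested separately in H1a and H1b. This stands too, and it is why the whole-circuit model should be kept. It does not make that model a test of H2b as the aims word it.

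A reader might infer that the extra connections dilute a true LPG signal and cost power. With independent connections and signal only in LPG connections at R² = 0.5, power was 80% with 9 features and 47% with 45. With a common correlation of 0.2 the loss all but vanishes: 39% with 9 against 44% with 45 at R² = 0.20, and 97% against 94% at R² = 0.5. Connections that share regions are unlikely to be independent, and the documents give no correlation structure, so a general power-loss claim is not supported.

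**Conclusion.** The point holds as an inconsistency between section 1 and section 17. Followed as written, section 17 does not test H2b as the aims state it, and a good fit need not involve LPG. This rests on the text and needs no simulation.

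The 36-of-45 share rests on the complete-graph assumption and should be quoted only with it. The voxel side cannot be sized.

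A reader might go further and infer that the SVR is specified to use every voxel and connection, or that an LPG-only model would prove LPG to be the source. The documents support neither. The first reads an omission as a statement. The second fails because H2b is an association across groups, and correlated connections can carry non-LPG signal into an LPG-only model.

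This is a mechanistic analysis of a secondary endpoint in a Stage 0 pilot. It should be corrected before the data are analysed, but it does not threaten the design or the sample size.

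**What to change.** Reconcile the two sections by defining the H2b features in section 17 as (a) change in task activation within an LPG mask, with voxel pattern or mean fixed in advance, together with (b) change in the connections between LPG and the other circuit regions. The same edit settles the mismatch between combining the two feature types and using one or the other.

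Report the whole-circuit and all-voxel models as separately labelled secondary analyses of the circuit–NPS relationship, not as evidence specific to LPG. State that the LPG-only model improves the match to the hypothesis without proving LPG specificity. Listing the circuit's connections would let readers see the true LPG share.

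The cost is a sentence or two in the analysis plan, with no new data. The downside is that a real non-LPG contribution appears only in the secondary models.

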Exploratory aim. Examine the relationship between (a) NPS and (b) the coherence between structural and functional aspects of the NPS-shared neural circuit. We will conduct a connectome-based analysis to find structural connections that are unique to severity of NPI. The TN-PCA method⁵³ will be used to correlate with severity of NPI. We can replace the high dimensional tensor network summarizing an individual's brain connectome with a K-dimensional vector of brain PC scores; these scores can be used for visualizing variation among individuals in their brain connectomes and in statistical analyses studying relationships between structural and functional aspects of NPS-shared circuit and covariates. We will compare similarities of involved brain regions of NPS circuit for FC and WM across the entire sample at baseline. Quantitatively, we will use the Dice similarity coefficient to evaluate the percentage of overlapped regions. **To examine whether tDCS' effects on NPS-shared neural circuit and study partner-rated NPS depend on baseline WM integrity,** first we will compare the correlations between FC (at different time points) and baseline WM integrity on the overlapped regions between active vs. sham tDCS groups. We expect to see a higher correlation between FC and WM in active group in later time points. Next, using SVR described earlier⁵² we will examine the relationship between the sample's features (baseline WM tracts) and outcome (change of NPI severity or frequency scores).

Blood analysis plan: We will compare AD pathology markers from blood with changes of NPS, cognitive measures, and MRI data using correlational analyses. We will also examine if individuals with positive AD pathology respond differently to tDCS compared to those with negative AD pathology using ANOVA.

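### H2b scores held-out SVR predictions by a measure blind to direction, so leave-one-out predictions that run the wrong way count as fit

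*Combined protocol and SAP*

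**What the plan says.** Section 17 (Data Analysis Plan), Aim 2, H2b specifies epsilon support vector regression with an RBF kernel in LIBSVM, pooled across groups. "The Leave-One-Out-Cross-Validation scheme will be applied", so every subject is the test case once. The features are "change of voxel activation from the task or change of FCs from the NPS-shared neural circuit after intervention", and the outcome is change in NPI severity or frequency. The scoring step is "We will then perform model fitting of the raw and predicted NPI using linear function" f(x)=ax+b, and adjusted R-squared "will be used to estimate goodness of fit for the model".

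The section gives no value for C, epsilon or gamma, no outcome scaling, no rule on the sign of a, no null distribution and no success threshold. The Exploratory aim in the same section reuses this SVR with baseline white-matter tracts as features and names no other score.

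In the sample-size paragraph, the circuit-to-NPI-Q association was r-squared 0.70 in an earlier study; "here we use a much more conservative estimation at" 0.20, giving n = 37 at power 0.80 and alpha 0.05. On dropout, "we estimate 10% attrition rate" from 40 subjects. The section also says: "Results from the study will provide information for accurately calculating effect size for future clinical trial".

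**The concern.** The R-squared of a line with free slope and intercept is the squared correlation between the two variables, whichever is on the x-axis. A model that predicts improvement for the subjects who worsened, and the reverse, earns the same score as one that predicts correctly.

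Leave-one-out makes this more than a technicality. Removing a subject with a high outcome lowers what the remaining subjects predict for that subject, and removing a low one raises it. With uninformative features, the held-out predictions therefore tend to correlate negatively with the outcome, and squaring turns that artefact into apparent fit.

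H2b is the analysis that ties change in the circuit to change in symptoms, which is the mechanistic claim of the study. At stake is whether its score can tell a moderate real association from none.

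**Working it through.** **The plan's own figure.** With r = √0.20 = 0.447 and atanh(0.447) = 0.481, two-sided 0.05 and power 0.80, n = ((1.960 + 0.842)/0.481)² + 3 = 36.9, so 37. This reproduces the plan and shows that n = 37 is the size for one bivariate correlation. It also supports reading 0.20 as a population value. At 40 × 0.90 = 36 completers, the power of that correlation test is 79%.

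**The score.** With one predictor, adjusted R-squared = 1 − (1 − r²)(n − 1)/(n − 2). At n = 36, r = +0.447 and r = −0.447 both give 1 − 0.80 × 35/34 = 0.176.

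**The negative lean.** A learner that ignores the features and predicts the training mean gives (n × mean − yᵢ)/(n − 1) for subject i. This falls as yᵢ rises, so r = −1 exactly and the planned R-squared is 1. The near-constant limit of epsilon-SVR (C = 0.000001, 500 data sets) gave r from −0.92 to −0.71, median −0.83.

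**Simulation inputs.** From the plan: leave-one-out, RBF epsilon-SVR, n = 36, r-squared 0.20 and 0.70, and ten regions (Section 1), hence 10 × 9/2 = 45 edges or 9 edges to the LPG. Assumed, because not stated: epsilon 0.1, gamma = 1/features, standardised outcome, C = 0.1, 1 or 10, and the signal structure. Voxel features were not simulated. Ranking is the probability that a signal data set outscores a null one. Power is taken at the score's own simulated one-sided 5% null cut-off.

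*Simulation A: edges that share regions, signal in the 9 LPG edges, 800 data sets per setting.* At r-squared 0.20 the planned score ranked 0.52 (C = 1) and 0.57 (C = 10) with 45 edges, and 0.56 and 0.59 with 9 edges. Repeat runs of 300 to 500 data sets gave 0.45 to 0.58. In one 300-data-set repeat the signed held-out correlation ranked 0.75 and 0.80 (45 edges) and 0.82 and 0.72 (9 edges); in another, 0.73 to 0.84 over all settings. At C = 0.1 the planned score ranked about 0.3.

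*Simulation B: independent or common-factor features, r-squared 0.20, 1,000 data sets per setting.*

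| Features, signal | C | Ranking, planned | Ranking, signed r | Power, planned | Power, signed r |
|---|---|---|---|---|---|
| 1 | 1 | 0.61 | 0.85 | 0.06 | 0.50 |
| 9, in one | 1 | 0.54 | 0.75 | 0.07 | 0.28 |
| 9, spread | 1 | 0.52 | 0.76 | 0.05 | 0.26 |
| 9, common factor | 1 | 0.54 | 0.77 | 0.06 | 0.30 |
| 45, spread | 1 | 0.43 | 0.65 | 0.03 | 0.17 |
| 45, common factor | 1 | 0.58 | 0.85 | 0.07 | 0.48 |
| 9, spread | 10 | 0.57 | 0.72 | 0.11 | 0.22 |
| 9, common factor | 10 | 0.55 | 0.70 | 0.09 | 0.18 |
| 9, spread | 0.1 | 0.33 | 0.69 | 0.02 | 0.22 |

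A shorter 400-run check of the one-feature case gave 0.66 for the planned score. With no signal, the 9-feature spread case at C = 1 had a negative slope in 68% of runs; at C = 0.1, in 94%.

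**Outcome scaling.** Leaving NPI change in raw points acts like a smaller C. With an assumed SD of 5, C = 1 is equivalent to 1/5 = 0.2 on the standardised scale, and the planned score ranked 0.33 (45 edges).

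**Strong signal (0.70).** In simulation A with 45 edges and C = 1, 10 or tuned, 96 to 99% of runs reached p<0.05, all with positive slope. In simulation B with 9 features at C = 1, ranking was 0.97. One exception was seen: 45 independent features with spread signal ranked 0.66 (signed correlation 0.93).

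**The case against.** **The slope is estimated, and H2b is directional.** An analyst would probably notice a negative a. This stands in part. In simulation A at C = 1 or 10, requiring a positive slope cut the null runs with p<0.05 from 15-26% to 2-6%. But the plan names adjusted R-squared as the measure and does not say to act on the sign.

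**The meaning of 0.20 is open.** If it means the held-out r-squared, separation is better. Population values of 0.40 and 0.45 gave mean held-out r of 0.47 and 0.41 (squares 0.22 and 0.17), planned-score ranking of 0.85 and 0.81, and power of 0.33 and 0.38. This stands as a limit on the size. The design value also concerns NPI-Q, not change in NPI.

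**A reader might infer that H2b has a false-positive rate of about 20%.** The documents do not support that. H2b has no p-value or threshold, so the share of null runs at p<0.05 (15-24% at C = 1 or 10 in one set of runs, 82-94% of those with negative slope) is only a marker.

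**A reader might infer that the effect sizes for the future trial are compromised.** That goes too far. The natural inputs to such a trial are the treatment contrasts in H1a, H1b and H2a, which do not use this score.

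**A reader might infer that the score fails at small C even for a strong signal.** This depends on the feature set. At C = 0.1 and r-squared 0.70, median adjusted R-squared was about 0.08-0.09 with 45 edges but 0.38-0.39 with 9. Section 1 describes an LPG-seeded circuit, which points towards 9.

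**Conclusion.** The concern holds for H2b and for the Exploratory aim's reuse of the SVR. That the score ignores direction follows from the text and needs no simulation; the negative lean under leave-one-out is what makes it matter.

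The size rests on assumed settings and on reading 0.20 as a population value. On that basis, at C of 1 or 10 the planned score ranks signal over no signal at about 0.5 to 0.6 (0.43 to 0.66 across individual runs). The signed correlation gives about 0.75 to 0.84 (0.65 to 0.85 across individual runs). At C = 0.1 the planned score is worse than a coin toss.

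The score is not useless in general: with a strong signal and C of 1 or more it worked in all but one setting run. Nor do the documents show that anti-prediction would be reported as support. They only leave nothing to prevent it. This should be corrected before analysis.

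**What to change.** - Make the signed correlation between held-out predicted and observed NPI change the H2b score. Attach one one-sided p-value, obtained by permuting the outcome through the whole leave-one-out loop, including any tuning.
- Count a zero or negative slope as no support for H2b.
- Report out-of-sample Q-squared = 1 − Σ(observed − predicted)² / Σ(observed − training mean)² beside it, as a description of prediction error only. It should not be a pass/fail rule: with 9 edges, C = 10 and true r-squared 0.20 its median was −0.15, and in one run requiring Q-squared above zero rejected 70% of true-signal data sets.
- Fix C, epsilon, gamma, feature set and outcome scaling in advance, or tune them inside each training fold.
- Use the same scoring in the Exploratory aim.

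**Cost.** This needs SAP wording and no new data. One untuned loop takes about 0.01 s, so 1,000 permutations take about 10 s; tuned over five values of C, about 0.2 s each, or 3 to 4 minutes. The reported fit will look less favourable. Power at r-squared 0.20 is low, roughly 15 to 50% depending on settings, so the 80% power behind n = 37 should not be attached to this analysis. Those power figures use a simulated null. The permutation procedure itself was run only with Q-squared as the score, where false support was 4.4 to 5.6%.

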Exploratory aim. Examine the relationship between NPS and the coherence between structural and functional aspects of the NPS-shared neural circuit. Cumulative literature suggests that white matter (WM) tracts play a critical role in supporting and shaping brain function.¹³ It is often assumed that FC is dependent on underlying anatomical connections,¹³⁻¹⁵ with decreases in WM integrity in dementia related to reduced functional efficiency.¹⁶ The magnitude of correlation between the structural and functional aspects of NPS-shared neural circuit may implicate the severity of NPS. Here, we will collect diffusion tensor imaging (DTI) at baseline, as part of MRI data acquisition, and examine whether the effects of tDCS on NPS-shared neural circuit and study partner-rated NPS depend on WM integrity. Exploring this question will provide broaden our mechanistic understanding of NPS.

We propose that probing the LPG via tDCS provides a way to experimentally test the causal relationship between our previously discovered NPS-shared neural circuit and study partner-rated NPS. The proposed research is highly innovative, while scientifically grounded, for targeting one brain region that may affect multiple NPS. Validating the hypotheses has the potential to support a future R01 study that directly conducts a Stage 2 trial addressing NPS in MCI or AD, thus ultimately improving patients' quality of life and reducing the caregiver burden.

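### The exploratory aim asks whether structure-function coherence relates to NPS, but no planned analysis relates a coherence measure to participants' NPS, and the Dice overlap has no chance reference

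*Combined protocol and SAP*

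**What the plan says.** Section 17 states the first exploratory aim as "Examine the relationship between (a) NPS and (b) the coherence between structural and functional aspects of the NPS-shared neural circuit". Section 1 gives the premise: "The magnitude of correlation between the structural and functional aspects of NPS-shared neural circuit may implicate the severity of NPS". Section 17 then lists four analyses.

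- Structural connectome: "The TN-PCA method⁵³ will be used to correlate with severity of NPI". The resulting component scores are also said to be usable in "statistical analyses studying relationships between structural and functional aspects of NPS-shared circuit and covariates".
- Regional overlap: "We will compare similarities of involved brain regions of NPS circuit for FC and WM across the entire sample at baseline", measured as follows: "we will use the Dice similarity coefficient to evaluate the percentage of overlapped regions".
- Structure-function correlation, by arm: "first we will compare the correlations between FC (at different time points) and baseline WM integrity on the overlapped regions between active vs. sham tDCS".
- Support vector regression (SVR), with baseline WM tracts as features and change in NPI severity or frequency as outcome.

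For the overlap, the plan gives no parcellation, no rule for how many connections or regions enter the WM set, and no value to expect by chance.

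**The concern.** The premise in section 1 is about people: those whose circuit shows a weaker or stronger match between structure and function may have more or less severe NPS. Testing it needs a coherence value that differs between participants, set against their NPI scores. The plan measures coherence in two places and uses NPI in two others, but never brings a coherence measure and participants' NPI together.

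Followed exactly, the plan would leave the question that heads this aim unanswered, although section 1 ties the DTI acquisition to it. A second problem is that the overlap figure cannot be judged large or small without knowing what random selection would give. The selected regions also carry forward, because the FC-WM correlations compared between arms are restricted to the overlapped regions.

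**Working it through.** **1. What each step brings together** (section 17, exploratory aim)

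| Step | Structure | Function | Related to participants' NPI |
|---|---|---|---|
| TN-PCA scores | yes | no | yes, severity |
| Dice overlap | yes | yes | no, one value for the whole sample |
| FC-WM correlation | yes | yes | no, compared by arm |
| SVR on WM tracts | yes | no | yes, change |

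No row has all three. A single Dice value has zero variance across the 40 participants, so no association with their NPI scores can be estimated from it. The text does not say whether the FC-WM correlations are taken within or across participants. On either reading the planned contrast is active against sham, not higher against lower NPI.

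**2. Dice expected by chance**

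Inputs: the circuit has 10 regions (section 1), hence 10 × 9 / 2 = 45 connections. Assumptions: the FC set is all 10 regions; WM connections are picked at random, unrelated to NPI; a whole-brain search covers 68 or 90 regions; 3 to 20 connections are picked. The plan gives none of these last figures.

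Dice = 2 × (regions in both sets) / (regions in FC set + regions in WM set).

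*Search confined to the circuit.* If the WM connections touch k of the 10 regions, Dice = 2k / (10 + k). A given region is missed when all j connections come from the 36 of 45 that do not touch it, so the expected k is 10 × (1 − C(36, j) / C(45, j)).

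- j = 3: 10 × (1 − 7,140 / 14,190) = 4.97, and 9.94 / 14.97 = 0.66
- j = 5: 10 × (1 − 376,992 / 1,221,759) = 6.91, and 13.83 / 16.91 = 0.82
- j = 10: 10 × (1 − 254,186,856 / 3,190,187,286) = 9.20, and 18.41 / 19.20 = 0.96

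Putting the mean of k into the ratio is an approximation. Simulation of 4,000 draws gives mean Dice of 0.66, 0.81 and 0.96.

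*Whole-brain search over M regions.* If k regions are drawn at random, expected Dice is 2 × (10k / M) / (10 + k). For k = 10 this is 0.15 at M = 68 and 0.11 at M = 90. Simulating random connections gives:

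| Regions searched | 5 connections | 20 connections |
|---|---|---|
| 68 | 0.14 | 0.22 |
| 90 | 0.11 | 0.17 |

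A Dice of 0.6, for example, would be below the chance average for a circuit-only search and far above it for a whole-brain one.

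**3. What 40 participants could show with a per-participant score**

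The plan states no sample size for this aim. Its nearest figure is n = 37 for r² = 0.20 at power 0.80 and alpha 0.05 (section 17). Taking alpha as two-sided, with r = 0.447 and atanh(r) = 0.481, n = ((1.960 + 0.842) / 0.481)² + 3 = 36.9, so 37. The stated figure is reproduced.

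The same approximation for a simple correlation of coupling with NPI gives:

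- Smallest |r| with 80% power at n = 40: tanh(2.802 / √37) = 0.43
- At n = 36 (10% fewer): tanh(2.802 / √33) = 0.45
- Power at r² = 0.20: 83% at n = 40 and 79% at n = 36

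**The case against.** Four points can be made on the other side.

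*The premise is not the commitment.* Section 1 goes on to promise an examination of whether tDCS effects depend on WM integrity, and the between-arm FC-WM comparison and the SVR serve that. This is fair for the second half of the aim. The first half, stated as the aim's title in both sections, still has no analysis.

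*Dice is not the only coherence measure.* A reader might infer that it is. The documents do not support that: the FC-WM correlation is a second measure, of the kind section 1 describes. It does not close the gap, because it is compared by arm.

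*Dice is not unrelated to NPS.* A reader might infer that it is blind to symptoms. In fact the WM connections are to be selected for their relation to NPI severity, and the FC circuit comes from earlier NPS work. The overlap therefore says something at group level about whether NPS-related structure coincides with the NPS-related circuit. What stands is narrower: one sample value cannot be related to individual scores.

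*Dice is not shown to be inflated.* A reader might infer that it is high by construction. That needs a search confined to the 10 regions, whereas the plan calls the WM step connectome-based, which points to the whole brain, where chance overlap is low. Nor does the plan say that Dice will be reported as evidence of coherence underlying NPS.

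The sentence on uses of the component scores does leave a route open, but it names no coherence index, model or NPS outcome.

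**Conclusion.** The concern holds as a mismatch between the aim and its analyses: no planned step relates a structure-function coherence measure to participants' NPS. This follows from the text and needs no assumption.

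The absence of a chance reference for Dice also holds, but its size is conditional. Average chance overlap is about 0.66-0.96 for a circuit-only search and about 0.11-0.22 for a whole-brain search, under the region and connection counts assumed above. The point is that the value cannot be interpreted until the search space is stated, not that it is known to be inflated.

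The weight is moderate. The aim is exploratory in a Stage 0 pilot, and Aims 1 and 2 are unaffected. Exploratory status excuses low precision. It does not excuse a set of analyses that leaves the stated question untouched when the data to address it are already being collected.

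**What to change.** Add to section 17, under the exploratory aim:

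1. **A per-participant baseline coupling score.** For each participant, compute the correlation, across the circuit's connections (45 for 10 regions), between that person's WM connection strength and resting FC.
2. **Its relation to NPS.** Relate the score to baseline NPI severity and report the estimate with a 95% CI, labelled exploratory. Age adjustment is optional.
3. **Dice as a descriptive figure.** State the search space and the rule that selects the WM connections. Report the observed Dice against its distribution when NPI scores are permuted across participants and the WM selection step is repeated each time.

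The cost is plan wording and modest computing. Baseline DTI, resting fMRI and NPI are already planned, so no visit or scan changes. The downside is one more exploratory estimate with a wide interval, which should be presented as such.
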